Study Objective(s)	
Primary To evaluate the usability of the FDA-approved RetinaVue Hand-Held 100 Camera in a population with multiple chronic conditions
 
Secondary
 
 • To evaluate pre-and-post-screening rates in the diabetic dialysis population. • To determine the proportion of overall retinopathy in a dialysis population • To evaluate participant satisfaction of screening utilizing the FDA-approved RetinaVue 100 hand-held camera
Study Design	This is a feasibility study.
Subject Population	Inclusion Criteria
key criteria for Inclusion and Exclusion:	
 • The subject must currently be seeking treatment for end-stage renal disease (ESRD) at one of the specified dialysis clinics. • The subject must be ≥ 18 years of age. 
Exclusion Criteria
 
 • The subject is <18 years of age.
Number Of Subjects	Up to 250 participants
Study Duration	
Each subject's participation may last up to 1 year.
 
The entire study is expected to last about 1 year.

Study Phases	(1) Screening for eligibility and obtaining consent, (2) Obtaining retinal images, completion of satisfaction survey, and medical record abstraction (3) For those participants recommended for referral, they will be given the opportunity to follow up with the remote provider.
Statistical And Analytic Plan	To assess usability of camera utilization, the primary objective, the proportion of inadequate images will be calculated.

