3 INVESTIGATIONAL PLAN

3.1 Study Design

This is a feasibility study to evaluate the usability of the FDA-approved RetinaVue 100 and contribute to knowledge about integrating telehealth into medical services.

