3.3 Study Population

Inclusion Criteria

- The subject must currently be seeking treatment for end-stage renal disease (ESRD) at one of the specified dialysis clinics.
- The subject must be ≥ 18 years of age.

Exclusion Criteria

- The subject is <18 years of age.

4 STUDY PROCEDURES (what will be done)

- Determine last documented retinal examination (electronic medical record)
- Determine cause of End-stage Renal Disease (ESRD) and vintage, I.e. how long patient has been on dialysis (paper chart)
- Determine patient demographics (electronic medical record)
 - DOS, DOB (age)
 - Gender, race
- Medical history (coronary artery disease, stroke, hypertension, if diabetes -duration)
- Medical labs (HbA1c, cholesterol, blood pressure)
- Smoking history
- Social determinants of health (education level, insurance status, etc).
- Check bilateral visual acuity with near card.
- Obtain bilateral retinal photographs with or without dilation.
- Complete the Usability survey.
- Complete the Participant Satisfaction survey.
- Upload patient images and metadata.
- Through the study PI, a board-certified ophthalmologist, interpret patient retinal images and return of diagnosis and management plan to dialysis unit including a wellness report to be given to individual subjects.
- Analyze data with biostatistician consultant
- Timeline. Quarter 1 (May –August 2016): Retinal image and metadata acquisition, clinic 1 and 2; Quarter 2 (September 2016-November 2016): retinal image and metadata acquisition clinic 3 and 4; Quarter 3 (December 2016-February 2017): data analysis; Quarter 4 (March 2017-May 2017): manuscript and presentation preparations.
- Subject results will be entered into the medical record. If something of note is found in a subject's

retinal scan, then staff at the dialysis clinic will provide follow up for any abnormalities found as part of clinical care.

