5 STUDY EVALUATIONS AND MEASUREMENTS

The following variables will be abstracted from medical records:

- Last documented retinal examination, cause of End-stage Renal Disease (ESRD) and vintage, I.e. how long patient has been on dialysis, DOS, DOB (age), gender, race, medical history (coronary artery disease, stroke, hypertension, if diabetes -duration), medical labs (HbA1c, cholesterol, blood pressure), smoking history, social determinants of health (education level, insurance status, etc).

Obtaining retinal images

- Nonmydriatic fundus images of both eyes were obtained from participants using the WelchAllyn RetinaVue™ 100 Imager. For those subjects with pupils smaller than 3 mm in either eye, a low dose dilation drop of 0.5% tropicamide will be administered to enlarge the pupil and assist in image capture. The images will be electronically sent via a HIPAA compliant portal to an offsite, board-certified ophthalmologist for remote interpretation. Following interpretation, a report will be generated that details any clinical findings and referral recommendations, which will then be distributed to individual subjects and uploaded to their electronic medical record. For those participants recommended for referral, they will be given the opportunity to follow up with the remote provider.

Participant satisfaction survey

- Participants will be asked to complete a brief participant satisfaction survey, which asks questions regarding their satisfaction with their exam experience. The survey utilizes a five-point Likert scale with responses ranging from strongly agree (1) to strongly disagree (5). The survey also allows for participants to provide qualitative observations about their experience. The survey asks about satisfaction of time to complete exam, comfort during the exam, comfort after the exam, first eye recovery after the camera flash, second eye recovery after the camera flash, and satisfaction with overall experience.

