6 STATISTICAL CONSIDERATION

6.1 Statistical Methods

Descriptive analyses will be used to assess demographic and medical history variables, camera usability, overall retinopathy, and participant satisfaction data. To assess usability of camera utilization, the proportion of inadequate images will be calculated. For participant satisfaction data, a response rate will be calculated followed by an overall mean score and standard deviation, and proportions for each of the six survey components. To assess overall retinopathy, a three-category outcome variable for retinopathy and referral at the individual level will be determined: (1) No retinopathy, (2) retinopathy without referral, and (3) retinopathy with referral. The following definitions will be determined (results for pairs of eyes will take into account that there may be some unreadable images): If the diagnosis in both eyes is no retinopathy then the individual has no retinopathy; otherwise, if either eye is considered severe, has proliferative diabetic retinopathy, clinically significant macular edema (CSME), or an inadequate image, the individual will be put into the retinopathy with referral category; likewise, if either eye is

mild/minimal or moderate retinopathy without CSME, then the individual will be placed into the retinopathy non-referral category.

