6.2 Sample Size and Power

The study aims to recruit and collect data from all individuals currently receiving treatment at the specified dialysis clinics. As such, the proposed sample (N=250) reflects the number of patients actively seeking treatment at those sites. Furthermore, this is a feasibility study and therefore 250 subjects is sufficient for the study team to determine the usability of the camera and to determine the prevalence of retinal disease in the dialysis population. In such a study, a power calculation is not indicated.

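### Participants with an inadequate image are counted as having retinopathy, which inflates the prevalence the study says it will determine

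*Combined protocol and SAP*

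**What the plan says.** Section 6.1 defines three person-level categories: no retinopathy, retinopathy without referral, and retinopathy with referral. A person has no retinopathy only if both eyes are read that way. Otherwise, severe disease, proliferative disease or clinically significant macular oedema in either eye leads to the third category, and the same sentence continues: "or an inadequate image, the individual will be put into the retinopathy with referral category". Section 6.1 also states that "results for pairs of eyes will take into account that there may be some unreadable images", but the either-eye assignment is the only rule it gives for doing so.

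Section 6.2 says that 250 subjects suffice, among other things, "to determine the prevalence of retinal disease in the dialysis population".

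On what happens after imaging, the Synopsis (Study Phases) and Section 5 both say: "For those participants recommended for referral, they will be given the opportunity to follow up with the remote provider". Section 4 adds that if something notable appears in a subject's "retinal scan, then staff at the dialysis clinic will provide follow up for any abnormalities found as part of clinical care". The list in Section 5 that opens "The following variables will be abstracted from medical records" includes the last documented retinal examination and background items. It has no item for attendance after referral or for the result of a later examination. Section 6.1 analyses none.

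**The concern.** An inadequate image carries no information about disease in that eye. Take a person with one eye read as normal and the other unreadable, or with both unreadable. Under Section 6.1 that person enters a category whose name and use say that retinopathy is present. The no-retinopathy category demands two normal readings, so every unreadable image moves people in one direction only.

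The result at stake is the secondary one, the proportion with retinopathy. It would mix disease seen on the image with failure of the image, and the mix would depend on how well the camera performs, which is the study's primary question. A clinic with poorer images would appear to have more retinopathy. No planned data item would let a reader separate the two afterwards unless the analysis keeps them apart.

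**Working it through.** **Plan's own figure.** N=250 in Section 6.2 is the number of patients treated at the four clinics. It comes from no formula, so there is nothing to reproduce.

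**Inputs.** From the documents: N=250 and the either-eye rule. Not in the documents, so assumed: true prevalence p of 20–50%; share u of participants with an inadequate image in at least one eye, 5–30%; inadequacy independent of disease; readable images graded correctly.

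**Step 1: reported against true proportion.** Under the rule, everyone with retinopathy plus everyone without it who has an inadequate image is counted as having retinopathy:

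reported = p + u(1 − p), so inflation = u(1 − p).

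Reported percentage, with inflation in points:

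| p | u = 5% | u = 10% | u = 20% | u = 30% |
|---|---|---|---|---|
| 20% | 24.0 (+4.0) | 28.0 (+8.0) | 36.0 (+16.0) | 44.0 (+24.0) |
| 35% | 38.25 (+3.25) | 41.5 (+6.5) | 48.0 (+13.0) | 54.5 (+19.5) |
| 50% | 52.5 (+2.5) | 55.0 (+5.0) | 60.0 (+10.0) | 65.0 (+15.0) |

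At p = 35% and u = 10%, 6.5/41.5 = 16% of those counted as having retinopathy would be there only because of an image.

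**Step 2: compare with sampling error.** The 95% half-width is 1.96 × √(p(1 − p)/250): 5.0 points at 20%, 5.9 at 35%, 6.2 at 50%. The inflation exceeds it in eight of the twelve cells.

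**Step 3: relax independence.** If q is the share with retinopathy among people with an inadequate image, inflation = u(1 − q). At u = 10% it runs from 0 (all diseased) to 10 points (none diseased). It cannot be negative.

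**Step 4: eyes to people.** If 10% of eyes are inadequate, u is 10% when the two eyes always fail together and 1 − 0.9² = 19% when they fail independently. A modest image failure rate can therefore affect a larger share of people.

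**Step 5: what separating the groups gives.** Take p = 35%, u = 10%, so 25 of 250 people have an inadequate image.

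- *No readable eye in any of the 25:* disease is seen in 0.35 × 225 = 78.75 people. Among gradable participants this is 78.75/225 = 35.0%. The bounds are 78.75/250 = 31.5% and (78.75 + 25)/250 = 41.5%.
- *One readable eye in all 25, showing the disease whenever it is present:* 8.75 are classed as retinopathy and 16.25 stay unresolved. The gradable proportion is 87.5/233.75 = 37.4%. The bounds are 87.5/250 = 35.0% and (87.5 + 16.25)/250 = 41.5%.

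The upper bound equals the plan's own figure in both cases. Section 6.1 as written therefore reports the upper bound as if it were the estimate.

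**The case against.** The best defence is that the third category is operational: it says who is sent on, and an unreadable image is a reason for sending someone on. Read that way the rule is coherent, and nothing here disturbs it. But the category is labelled retinopathy, is introduced as the means of assessing overall retinopathy, and feeds a stated prevalence aim. For that use the defence fails.

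It can also be said that the size is assumed throughout. That stands: the documents give no inadequate-image rate, and if nearly all images are readable the effect is small. Only the direction is certain. Finally, this is a feasibility study and the issue concerns a secondary result. That also stands, and limits the weight of the point.

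A reader might infer something stronger: that because follow-up is a named study phase yielding no data, the image findings are never checked and the study fails for want of confirmation. The documents do not support this.

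- Images go "to an offsite, board-certified ophthalmologist for remote interpretation", so they are read by a specialist. What is absent is a recorded comparison with an in-person examination.
- Follow-up is described as an opportunity and as clinical care, and a study phase need not produce an outcome.
- Confirmation of referrals is not an objective. The statement that the study will "contribute to knowledge about integrating telehealth into medical services" is a general aim, not an endpoint.
- Recording follow-up would not cure the prevalence figure. It would cover only referred people who chose to attend, and would leave the other two categories unexamined.

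**Conclusion.** The concern holds as a misclassification in Section 6.1: people who are only ungradable are counted as having retinopathy, and no planned data establish their true status. Under the assumed ranges and independence, the inflation is about 2.5 to 24 points; at 35% prevalence and 10% inadequate it is 6.5 points, slightly more than the sampling half-width. That half-width assumes all 250 enrol and are treated as a sample from a wider dialysis population.

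The conclusion does not extend to the primary measure, the proportion of inadequate images, which needs no disease status. Nor does it make the lack of follow-up data a failing in itself.

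**What to change.** In Section 6.1, separate referral for an inadequate image from retinopathy, for analysis only:

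1. If one eye is inadequate and the readable eye shows retinopathy, classify the participant by the readable eye. Otherwise, classify a participant with an inadequate image as ungradable (unresolved).
2. Report the number ungradable and the retinopathy proportion among gradable participants.
3. Give bounds over all imaged participants, counting the unresolved first as without and then as with retinopathy.
4. Describe the result as camera-detected (image-based) in Sections 6.1 and 6.2.

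Clinical referral stays as the plan has it. The cost is a little analysis work, a smaller denominator and a wider stated range. In the first case of Step 5, the half-width rises from 5.9 points (250 people) to 6.2 (225 people). The gradable proportion also keeps some upward lean, because one-eye positives are retained while one-eye negatives become unresolved. At 35% and 10% this is at most 37.4 − 35.0 = 2.4 points, against 6.5 now, and it is why the bounds should always accompany the figure.

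Optionally, abstract attendance and examination findings for referred participants from the medical record and report them separately, as descriptive results among attenders. Do not merge them into the main proportion: attenders select themselves, the proportion would then combine two methods of ascertainment, and an examination elsewhere may not appear in the record. The cost is a second chart look-up for the referred group.

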1 BACKGROUND AND RATIONALE

1.1 Introduction

There are no studies evaluating (diabetic or non-diabetic) retinopathy in the renal dialysis patient population (~300,000 Americans). Approximately 50% of this population has End-stage Renal Disease (ESRD) due to diabetes. Dialysis patients are among the most debilitated patients, and thus, have even more barriers to receiving their recommended annual retinal evaluation. The advent of the RetinaVue hand-held retinal camera holds great promise in this population, as dialysis patients access medical care 3 times a week, for several hours at a time at their dialysis clinic.

1.2 Non-Clinical and Clinical Study Findings

Potential Benefits:

The potential benefits to subjects from being in this study may include receiving a screening of their eyes, a diagnosis, and potential follow up that they may not have received unless they were in the study.

Risk /Benefit Assessment:

A possible side effect expected would be temporary discomfort in the eye/s due to the camera flash. This is seen infrequently in the clinical setting and should not last more than 2-3 minutes.

As part of the eye exam, drops may be put in the eyes to dilate the pupils. The drops may blur vision and make the subject sensitive to light. The drops will wear off over several hours. There is a small risk of an allergic reaction to the drops. There is also a small risk that the drops could cause the eye pressure to rise. If this happens, it will be treated, but there is a small risk of losing vision from the pressure rise. Due to the blurring effect on vision and possible light sensitivity, we will recommend that the subject not drive until the blurring effects of the drops have worn off. If necessary, the subject should have someone with them who can drive for them after the exam.

There may be uncommon or previously unknown risks.

2 STUDY OBJECTIVE

Primary Objective:

- To evaluate the usability of the FDA-approved RetinaVue Hand-Held 100 Camera in a population with multiple chronic conditions

Secondary Objective

- To determine rates of overall retinopathy in a dialysis population
- To evaluate participant satisfaction of screening utilizing the FDA-approved RetinaVue 100 hand-held camera

3 INVESTIGATIONAL PLAN

3.1 Study Design

This is a feasibility study to evaluate the usability of the FDA-approved RetinaVue 100 and contribute to knowledge about integrating telehealth into medical services.

3.2 Study Duration, Enrollment and Number of Subjects

The study team anticipates the study duration to be about 1 year.

This study will recruit participants from four UNC outpatient dialysis clinics in the following locations: Carrboro, Siler City, Pittsboro, and Mebane, North Carolina.

The study proposes enrolling up to 250 subjects across all four study sites.

3.3 Study Population

Inclusion Criteria

- The subject must currently be seeking treatment for end-stage renal disease (ESRD) at one of the specified dialysis clinics.
- The subject must be ≥ 18 years of age.

Exclusion Criteria

- The subject is <18 years of age.

4 STUDY PROCEDURES (what will be done)

- Determine last documented retinal examination (electronic medical record)
- Determine cause of End-stage Renal Disease (ESRD) and vintage, I.e. how long patient has been on dialysis (paper chart)
- Determine patient demographics (electronic medical record)
 - DOS, DOB (age)
 - Gender, race
- Medical history (coronary artery disease, stroke, hypertension, if diabetes -duration)
- Medical labs (HbA1c, cholesterol, blood pressure)
- Smoking history
- Social determinants of health (education level, insurance status, etc).
- Check bilateral visual acuity with near card.
- Obtain bilateral retinal photographs with or without dilation.
- Complete the Usability survey.
- Complete the Participant Satisfaction survey.
- Upload patient images and metadata.
- Through the study PI, a board-certified ophthalmologist, interpret patient retinal images and return of diagnosis and management plan to dialysis unit including a wellness report to be given to individual subjects.
- Analyze data with biostatistician consultant
- Timeline. Quarter 1 (May –August 2016): Retinal image and metadata acquisition, clinic 1 and 2; Quarter 2 (September 2016-November 2016): retinal image and metadata acquisition clinic 3 and 4; Quarter 3 (December 2016-February 2017): data analysis; Quarter 4 (March 2017-May 2017): manuscript and presentation preparations.
- Subject results will be entered into the medical record. If something of note is found in a subject's

retinal scan, then staff at the dialysis clinic will provide follow up for any abnormalities found as part of clinical care.

5 STUDY EVALUATIONS AND MEASUREMENTS

The following variables will be abstracted from medical records:

- Last documented retinal examination, cause of End-stage Renal Disease (ESRD) and vintage, I.e. how long patient has been on dialysis, DOS, DOB (age), gender, race, medical history (coronary artery disease, stroke, hypertension, if diabetes -duration), medical labs (HbA1c, cholesterol, blood pressure), smoking history, social determinants of health (education level, insurance status, etc).

Obtaining retinal images

- Nonmydriatic fundus images of both eyes were obtained from participants using the WelchAllyn RetinaVue™ 100 Imager. For those subjects with pupils smaller than 3 mm in either eye, a low dose dilation drop of 0.5% tropicamide will be administered to enlarge the pupil and assist in image capture. The images will be electronically sent via a HIPAA compliant portal to an offsite, board-certified ophthalmologist for remote interpretation. Following interpretation, a report will be generated that details any clinical findings and referral recommendations, which will then be distributed to individual subjects and uploaded to their electronic medical record. For those participants recommended for referral, they will be given the opportunity to follow up with the remote provider.

Participant satisfaction survey

- Participants will be asked to complete a brief participant satisfaction survey, which asks questions regarding their satisfaction with their exam experience. The survey utilizes a five-point Likert scale with responses ranging from strongly agree (1) to strongly disagree (5). The survey also allows for participants to provide qualitative observations about their experience. The survey asks about satisfaction of time to complete exam, comfort during the exam, comfort after the exam, first eye recovery after the camera flash, second eye recovery after the camera flash, and satisfaction with overall experience.

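### Do the label "nonmydriatic" and the unsplit image-adequacy figure require a change when some subjects receive dilating drops?

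*Combined protocol and SAP*

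**What the plan says.** Section 5, under the heading on retinal images, opens with "Nonmydriatic fundus images of both eyes were obtained from participants". The next sentence reads "For those subjects with pupils smaller than 3 mm in either eye, a low dose dilation drop of 0.5% tropicamide will be administered", and gives the purpose as "to enlarge the pupil and assist in image capture". Section 4 lists the imaging step as "Obtain bilateral retinal photographs with or without dilation", and the risk text in Section 1.2 warns that drops may be used and describes their after-effects.

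The synopsis and Section 6.1 measure camera usability, the primary objective, by one proportion of inadequate images. Section 6.1 places this under descriptive analyses and names no subgroup.

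On data capture, Section 5 lists chart variables under "The following variables will be abstracted from medical records" and describes the satisfaction questionnaire ("The survey asks about satisfaction of time to complete exam, comfort during the exam, comfort after the exam", followed by flash recovery in each eye and overall experience). Neither list contains dilation status or pupil size. Section 4 also includes "Upload patient images and metadata" and "Complete the Usability survey", without giving the contents of either. Section 8 mentions a spreadsheet but not its fields.

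**The concern.** Three things look wrong together. The images are called nonmydriatic although some are taken after a mydriatic. Drops are given to help capture, so they act directly on the quantity that the primary measure counts. And the plan neither names a field for dilation status nor plans to report adequacy separately with and without drops.

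How often drops are needed is part of whether a hand-held camera suits a dialysis clinic. Section 1.2 says that the drops take several hours to wear off and that subjects will be advised not to drive until the blurring has cleared. Section 3.1 wants the study to inform the use of telehealth in medical services. If dilation went unrecorded at imaging it might not be recoverable, and the report could then give one adequacy figure without saying how much of it depended on drops. A reader who took the Section 5 label at face value could credit that figure to undilated photography.

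**Working it through.** **1. The statements on drops, side by side.**

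| Place | What it implies |
|---|---|
| Section 5, first sentence | Undilated imaging of both eyes |
| Section 5, second sentence | Drops if either pupil is under 3 mm |
| Section 4 | Either condition is allowed |
| Section 1.2 | Drops are possible; risks are described |

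The last three agree. Only one word in the first sentence is out of line, and the sentence after it supplies the exception. Whether a subject with one small pupil has one or both eyes treated is not stated. That is a gap, not a contradiction.

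**2. Where dilation status would be recorded.** The two lists that can be read are a chart-abstraction list and a set of experience questions. Neither is a natural home for pupil size or drops given at imaging. The natural homes are the image metadata and the Usability survey, and their contents are not shown. Capture is therefore unconfirmed. It has not been shown to be missing.

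**3. What the pooled figure measures.** Let s be the dilated share, p_d the inadequate proportion with drops and p_u the proportion without:

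pooled = s·p_d + (1 − s)·p_u

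The documents give none of the three, so these values are assumed for illustration:

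- s = 0.5, p_d = 0.30, p_u = 0.10: 0.5 × 0.30 + 0.5 × 0.10 = 0.20.
- s = 0.5, p_d = 0.10, p_u = 0.30: 0.5 × 0.10 + 0.5 × 0.30 = 0.20.

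The pooled 20% does not reveal which component is worse. It is nevertheless the proportion inadequate under the procedure as run, which is what the primary objective asks for.

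**4. What a split would deliver.** Inputs: N = 250 (Section 6.2); two eyes each, so up to 500 eyes; assumed shares given drops of 10%, 30% and 50%, so k = 25, 75 and 125 participants; assumed 20% inadequate. The eye is taken as the unit, which is a further assumption because Section 6.1 speaks only of images. The Wilson 95% half-width, with z = 1.96, is

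h = z·√[p(1−p)/n + z²/(4n²)] / (1 + z²/n)

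For the dilated group, effective n runs from k (one eye each, or two fully correlated eyes) to 2k (two independent eyes). For the undilated group the table uses n = 250 − k, the case where both eyes of the k participants are dilated and the remaining pairs are fully correlated.

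| Share given drops | h for that share (n = 250) | h, dilated group | h, undilated group |
|---|---|---|---|
| 10% | 3.7 points | 10.9 to 15.1 | 5.2 |
| 30% | 5.6 points | 6.4 to 8.9 | 5.9 |
| 50% | 6.2 points | 4.9 to 7.0 | 7.0 |

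Overall, with effective n from 500 down to 250, h is 3.5 to 4.9 points. If some subjects had one eye treated and others both, with fully correlated eyes, effective n could fall to about 0.89k. The upper ends for the dilated group would then be about 16.0, 9.5 and 7.4.

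These figures describe the precision of an additional table. They do not measure an error in the plan. The share of participants given drops would be well estimated from a single yes/no flag. The adequacy split would be imprecise if drops were uncommon.

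**5. What a split could mean.** Drops are assigned by pupil size, so dilated and undilated eyes differ before any drop is given. The difference between the groups would not estimate the effect of dilation.

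**The case for a change.** The best case for a change is that this is cheap now and may be impossible later. Up to two fields per eye and one descriptive table would settle it, with the primary measure and the sample size untouched. Dilation is a passing event that a chart review may not recover, and the documents do not show that anyone writes it down. The need for drops bears on practicality in a dialysis unit, and the pooled figure cannot display it. If the Section 5 sentence were carried into the manuscript, it would misdescribe some of the images.

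Much of this is fair. The label is literally inaccurate for subjects given drops, no breakdown is named, and it would be sensible to state how many participants received drops next to the primary proportion. But the loss depends on non-recording, which is not established. Descriptive reporting of usability under Section 6.1 already has room for the share given drops. Sections 4 and 5 do not conflict on drops, so there is nothing between them to reconcile. The further step, adequacy by dilation status, answers no stated objective and could invite readers to see a dilation effect that the data cannot support.

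**Conclusion.** No change to the plan is needed. The word at issue is a wording slip, corrected in effect by the next sentence and by Sections 1.2 and 4. It alters nothing that the study does or concludes. Followed as written, the plan gives a sound estimate of the proportion of inadequate images under a procedure that uses drops for small pupils.

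No bias in that estimate is shown, and none can be sized, because the documents give neither the share dilated nor an inadequate rate. The half-widths above rest on assumed shares of 10% to 50%, an assumed 20% inadequate and the eye as unit. They show only what an optional table could resolve.

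Two things depend on ordinary good practice: that dilation status is noted at imaging, and that the report describes the images accurately and says how many participants had drops. The protocol leaves room for both. This conclusion takes no view on the dilation rule itself.
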